### **Data Collection Procedures**

Electronic data from medical monitoring devices, including BIS™ and PMD-200™, will be collected. Before collecting any data, all device times will be time-synchronized. The time of anesthesia induction, intubation, surgical incisions, and other intraoperative events will be manually recorded. This computer gathers all the data electronically and uses the integrated events tag system of the Medasense PMD-200™, or the BetterCare software (provided by Dräger, Lübeck, Germany) connected to the Dräger anesthesia workstation.

All anesthesia and surgery-related events, like the type and amount of vasopressor used, will be recorded separately on a Case Report Form (CRF). The CRF will be built using RedCap software (Vanderbilt University), which will be accessed via electronic tablets by the research team in the operating room. Once the anesthesia is complete and the patient extubated, all the electronic data will be exported.

The data from various monitor devices (anesthesia workstation, ventilator, BIS Index, NOL Index), as well as raw waves form of specific signals (BP, pulse-oximetry, plethysmography, EKG), will be electronically extracted under a unique identification number assigned at randomisation, to a secured, offline research computer, insuring patient anonymization. Patient identity will only be mentioned on the consent form, which will be kept in a locked closet in the Department of Anesthesiology at Maisonneuve-Rosemont Hospital for as long as required by the law (15 years).

Pain intensity is recorded according to a verbal numerical rating scale (0 = absence of pain, and 10 = unbearable pain).

Opioid requirements, pain scores, and post-operative events such as PONV and critical respiratory events will be documented on the PACU record.

## **E. STATISTICAL PLAN**

### **Sample Size Determination and Power**

Based on a recent unpublished trial (MERK study) recently held at our center focusing on colorectal surgeries, we assumed a mean intraoperative remifentanil consumption of 5.59 mcg.kg-1.h-1 and 7.98, respectively in the intervention and control group, with a combined standard deviation of  $\pm 3.24$ . This data is aligned with recently published international data (Sabourdin et al., 2022). With an alpha risk of 5%, a power of 80.0%, a two-tailed test, and an estimated dropout ratio of 10.0%, it was calculated that 32 patients would be required in each group, to detect a 30% reduction in intraoperative remifentanil administration.

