## **Hypotheses**

The main hypothesis of this study is to show that patients receiving an intraoperative esmolol infusion during a NOL-guided general anesthesia, will consume a lower amount of intraoperative remifentanyl (mcg.kg-1.h-1) with a reduction of 20 to 30% of intraoperative opioid consumption, without impacting hemodynamic parameters. Upon reproducible nociceptive stimulation such as orotracheal intubation and initial surgical incision, we expect a reduction of the deltaNOL with the administration of esmolol, while still capturing the event on the PMD-200. Finally, once the patient reaches the PACU, we expect a longer time to first opioid, a lower pain score on arrival, a lower opioid consumption, a reduced incidence of PONV, and a shorter PACU stay.

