### **Statistical Methods**

Descriptive statistics will be presented by groups using mean and standard deviation, or median and interquartile range if the distribution is skewed or not normal for continuous parameters (according to the skewness of the distribution of each parameter). Frequency (%) will be used for categorical parameters. According to the nature of the analyzed endpoints, confidence intervals (CIs) between proportions or between means/medians differences will be presented. Missing data will be replaced by the maximum value observed (worst-case scenario). Risk differences or mean differences with 95% confidence intervals will be reported for all outcomes. The alpha value will be set at 0.05 to establish statistical significance. All data will be analyzed by the intention to treat principle. All statistical analysis will be performed using SAS, SPSS software or python programming language via VS Code or Jupyter notebook software.

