### *Primary Outcome*

Total dose of remifentanil in mg.kg-1.h-1 will be compared using Wilcoxon Mann-Whitney test (assuming data will not necessarily follow a normal distribution).

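### The stated 80% power belongs to a comparison of means with dropouts removed, not to the Wilcoxon, intention-to-treat, maximum-value analysis that the protocol specifies

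*Protocol*

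**What the plan says.** Protocol, Sample Size Determination and Power: "we assumed a mean intraoperative remifentanil consumption of 5.59 mcg.kg-1.h-1 and 7.98, respectively in the intervention and control group". The SD used for both arms together is 3.24. At an alpha of 5%, the section goes on to state "a power of 80.0%, a two-tailed test, and an estimated dropout ratio of 10.0%, it was calculated that 32 patients would be required in each" arm. The target effect is given there as a 30% reduction.

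Protocol, Primary Outcome: the remifentanil dose rate "will be compared using Wilcoxon Mann-Whitney test (assuming data will not necessarily follow a normal distribution").

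Protocol, Statistical Methods: "Missing data will be replaced by the maximum value observed (worst-case scenario"). The same paragraph says that all data are analysed by intention to treat.

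Three other sections treat lost patients differently. Exclusion criteria removes patients after recruitment if they withdraw consent or are converted to laparotomy. When and How to Withdraw Patients counts conversion and an unstable NOL signal as withdrawals. Data Collection and Follow-up for Withdrawn Patients keeps no data after withdrawal.

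The Hypotheses section expects the intervention to lower remifentanil use "with a reduction of 20 to 30% of intraoperative opioid consumption".

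**The concern.** The 10% allowance in the sample size treats dropouts as patients who leave the analysis, so that about 29 per arm remain and are compared cleanly. The Statistical Methods section keeps them in and gives each one the highest dose seen. In a rank test these patients tie at the top of both arms. They carry no information about the treatment and they pull the two arms together. Adding patients to replace dropouts does not cover that dilution.

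Two things are at stake. The 80% on which the trial is justified may not describe the analysis that will be run. Also, if losses fall unevenly, the rule acts directly on the comparison, because every missing esmolol patient is scored as a maximal remifentanil user. The Breach of protocol section allows the protocol to be stopped for haemodynamic instability, and the protocol lists hypotension and bradycardia among esmolol's known reactions, so uneven loss is conceivable.

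**Working it through.** **Inputs from the protocol.** Means 7.98 (control) and 5.59 (esmolol), SD 3.24, two-sided 5%, power 80%, dropout 10%, 1:1 allocation, 32 per group.

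**Step 1: reproduce 32.**
- Difference = 7.98 - 5.59 = 2.39, which is 2.39/7.98 = 29.95% of the control mean. Standardised effect d = 2.39/3.24 = 0.738.
- n per arm = 2(1.960 + 0.842)²/d² = 28.85, rounded up to 29.
- 29 x 1.10 = 31.9, so 32. Also 28.85/0.9 = 32.05.

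The stated figure is therefore a normal-approximation comparison of means with dropouts removed. At 29 completers its power is 80.2% (normal approximation) or 78.8% (t-test).

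**Step 2: why the maximum-value rule costs power.** With normal data, the chance that a random control patient has a higher rate than a random esmolol patient is Φ(0.738/√2) = 0.699, which is 0.199 above the null value of 0.5. If 10% of each arm are tied at the top, this becomes about 0.81 x 0.699 + 0.09 + 0.01 x 0.5 = 0.661. The excess is then 0.161, or 0.81 of what it was. For 32 per arm the null standard error is √(65/(12 x 32²)) = 0.0727. The excess falls from 0.199/0.0727 = 2.74 to 0.161/0.0727 = 2.22 standard errors. Approximate power falls from Φ(2.74 - 1.96) = 78% to Φ(2.22 - 1.96) = 60%. Simulation gives slightly higher values and the same pattern.

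**Step 3: simulation.** Wilcoxon test (asymptotic, two-sided 5%), the protocol's means, and missing values set to the pooled observed maximum. Most cells use 20,000 simulated trials. These assumptions are not in the protocol: the distribution shape, equal loss in both arms unless stated, and all 10% lacking the endpoint unless stated. Where a cell has two figures, the first is for exactly 3 missing per arm and the second for a random 10%.

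| Data | 32 per arm, none missing | 29 completers | 32 per arm, 10% set to maximum |
|---|---|---|---|
| Normal, common SD | 81% | 76.5% | 66% / 62% |
| Gamma, common SD | 88% | 84% | 76% / 70.5% |
| Lognormal, common SD | 93% | 91% | 83% / 78% |
| Gamma, equal CV, pooled SD 3.24 | 80% | 76% | 66% / 62% |
| Lognormal, equal CV, pooled SD 3.24 | 86% | 83% | 74% / 67% |

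**Step 4: vary the missingness.**
- One missing per arm: about 76-91% across these shapes.
- A random 5% missing (common SD): 71% normal, 79% gamma, 86% lognormal.
- Five missing on esmolol and one on control (common SD): about 24% normal, 34% gamma, 45% lognormal.

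**Step 5: the lower end of the hypothesis.** A 20% reduction is 0.20 x 7.98 = 1.596. T-test power is about 45% with 29 per arm and 49% with 32.

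**The case against.** The strongest reply is that nothing is miscalculated, and that is right. A reader might infer that 32 is an arithmetic error or that the dropout inflation is wrong. The documents do not support this. The figure reproduces, and using 29/0.9 or the t-test n of 30 moves it by only one or two patients per arm.

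The second reply is that the largest losses rest on unstated inputs. This also stands. The sections on exclusion and withdrawal point to removing dropouts, which agrees with the sample size calculation and leaves Wilcoxon power at about 76-91%. Some dropouts may still have a usable endpoint. The endpoint is a rate, and withdrawal of consent is described as occurring before anaesthesia or in the PACU, outside the period in which the endpoint accrues. A dose rate also cannot be negative, so normal data are a rough model, and lognormal data with a common SD stay near 80% even under the maximum rule. Statistical Methods does not say whether the maximum is pooled or taken within arm. The within-arm version with three missing gives about 70% (normal), 78% (gamma) and 83% (lognormal, common SD).

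Skew does not settle the matter, though. Gamma data fall below 80% under the rule at 10% missing, and so do lognormal data with equal CV. The exclusion and withdrawal sections do not override intention to treat. They contradict it, so the protocol leaves open which analysis the 80% describes.

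The third reply is that the sample size section already says that it is built for a 30% reduction. That is correct.

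**Conclusion.** The concern holds as a mismatch between the power calculation and the specified primary analysis. The change of test alone costs about two points with normal data (81% against 83% by t-test with all 32 observed). The maximum-value rule causes most of the loss. If the assumed 10% per arm lack the endpoint and are set to the pooled maximum, power for the 30% effect is about 62-66% (normal), 70-76% (gamma) or 78-83% (lognormal, common SD). With equal CV, gamma and lognormal data give 62-74%. With one missing per arm the range is about 76-91%, so the shortfall may be small. Its size depends on the distribution shape and on how many dropouts truly lack the endpoint, and the protocol gives neither.

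A reader might go further and conclude that the trial simply has about 62% power. That is one corner of the range and not an established value. A reader might also treat the 20% end of the hypothesis as a design error. It is not, because the target of 30% is stated openly. Power of about 45-49% at 20% is only a caution: a non-significant result would say little against a reduction of that size.

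**What to change.** 1. Take the maximum-value rule off the primary analysis, and keep it as a sensitivity analysis at most.
2. For every randomised patient with data, analyse the remifentanil rate recorded from incision up to any conversion, NOL failure or protocol stop. With all 32 per arm contributing, Wilcoxon power is about 81% on normal data. Each endpoint that is truly lost lowers this a little, down to about 76% with 29 per arm.
3. Reconcile Exclusion criteria and the two withdrawal sections with the intention-to-treat statement, so that one population is defined and the handling of data collected before withdrawal is clear.
4. If the maximum-value rule is kept for the primary endpoint, restate the power for that analysis with the range above and its assumptions, and say whether the maximum is pooled or within arm. For reference, 80% with a random 10% missing would need about 48 per group (normal), 40-42 (gamma, common SD) or 34-35 (lognormal, common SD).
5. When a null result is interpreted, note the limited power at the 20% end.

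The cost is wording in the protocol, and in any statistical analysis plan that repeats it. Items 1 to 3 need no extra patients. Item 4 needs none either, unless the sponsor wants to restore 80%, but the stated power would be less favourable in most of the cases examined.

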### **Statistical Methods**

Descriptive statistics will be presented by groups using mean and standard deviation, or median and interquartile range if the distribution is skewed or not normal for continuous parameters (according to the skewness of the distribution of each parameter). Frequency (%) will be used for categorical parameters. According to the nature of the analyzed endpoints, confidence intervals (CIs) between proportions or between means/medians differences will be presented. Missing data will be replaced by the maximum value observed (worst-case scenario). Risk differences or mean differences with 95% confidence intervals will be reported for all outcomes. The alpha value will be set at 0.05 to establish statistical significance. All data will be analyzed by the intention to treat principle. All statistical analysis will be performed using SAS, SPSS software or python programming language via VS Code or Jupyter notebook software.

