***Anesthesia maintenance during surgery:***

Nociception management: The remifentanil target controlled infusion will be set at 3 ng.ml prior to the surgical incision, and will be modified according to the NOL index, as described in Figure 1. If the NOL index is > 25 for more than 1 min, we will increase remifentanil TCI by 0.5 ng.ml. This rate will be decreased by steps of 0.25 ng.ml if the NOL index is < 10 for more than 3 min. The minimal remifentanil TCI concentration allowed in the protocol will be 1 ng ml, to ensure a minimal antinociception drug administration in case of inaccuracy of NOL

Index in either group. Furthermore, in the event of a TAM > 120% of its basal level, and despite a NOL Index between 10 and 25, remifentanil will be increased.

Only the **intervention** and **anesthesia maintenance** sections above differ from the usual management of patients under general anesthesia.

In both groups, IV hydromorphone 0.006 mg.kg and ondansetron 4 mg will be administered once pneumoperitoneum is deflated and skin suture is started. Local anesthetic infiltration of the wounds will be performed by the surgical team using a maximum of 30 ml de bupivacaine 0.5%. Remifentanil infusion will be stopped and removed at the start of wound dressing.

Hemodynamic management: Baseline mean arterial blood pressure (MAP) will be defined as the average of three consecutive values taken 1 min apart and determined before the induction of general anesthesia. Intravenous (IV) infusion of norepinephrine will be adjusted to maintain +/- 20% of the baseline values of the pre-anesthesia MAP. Balanced crystalloids will be administered to patients at a rate of 3 ml.kg.h (ABW) throughout the surgery. Intravenous fluid boluses will be administered at the discretion of the anesthesiologist in charge. Perioperative blood management will be done according to guidelines.

Depth of anesthesia management: The maintenance of anesthesia will rely on sevoflurane to reach [0.7–1.2] minimal alveolar concentration (MAC; MAC adjusted to the participant's age) and a BIS index of [40-60]. Sevoflurane will be discontinued when the wound dressing is completed, and participants will be extubated in the operating room and transferred to the post-anesthesia care unit (PACU).

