## **D. ENDPOINTS**

### **Primary endpoint**

The primary endpoint is the intraoperative amount of remifentanyl in mcg.kg-1.h-1, administered between the first surgical incision and its discontinuation at wound dressing.

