### **Secondary endpoints**

- The NOL Index variation before and after orotracheal intubation and first surgical incision. NOL index will be evaluated 3 minutes after stimulation to record the maximum value and calculate the area under the curve;
- The mean intraoperative BP and HR;
- The intraoperative doses and time weighted average of norepinephrine (mg); ephedrine (mg), glycopyrrolate (mg) and atropine (mg);
- Total time and time weighted average with NOL value above > 25;
- The total time and time weighted average of hypotension (< 20% of the baseline values of the pre-anesthesia mean arterial pressure (MAP) and/or bradycardia (HR < 60 beats/min, or HR < 50 beats/min for a profound bradycardia)) during surgery;
- The time to first analgesic requirement in PACU;
- The amount of morphine equivalent consumption for postoperative pain relief in the post anesthesia care unit (PACU) in both groups.
- The intensity of pain at rest and under stress, using a verbal rating scale (VRS), from arrival to discharge from PACU.

- The Silvermann Integrated Approach (SIA) Score (combining pain score and opioid consumption);
- Postoperative outcomes such as postoperative nausea and vomiting (PONV) and amount of antiemetics used in PACU;
- The time spent in PACU (in minutes);

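### One maximum-value rule for all missing data is called worst case, but it is the best case for time to first analgesic and is not reliably conservative for the primary comparison

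*Protocol*

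**What the plan says.** The protocol's Statistical Methods section states: "Missing data will be replaced by the maximum value observed (worst-case scenario". It makes no distinction by endpoint or arm, and does not say whether the maximum is taken over all patients or within an arm. The same paragraph commits the trial to intention to treat.

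The endpoints under this rule point in different directions:

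- **Primary endpoint:** remifentanil per kg per hour, "administered between the first surgical incision and its discontinuation at wound dressing". Lower is better.
- **A secondary endpoint:** "The time to first analgesic requirement in PACU". The Hypotheses section says of esmolol patients in PACU that "we expect a longer time to first opioid". Higher is better.
- **Another secondary endpoint:** "The mean intraoperative BP and HR". The Hypotheses section expects the opioid saving "without impacting hemodynamic parameters", and under hemodynamic management norepinephrine "will be adjusted to maintain +/- 20% of the baseline values of the pre-anesthesia MAP". Neither extreme is named as the bad one.

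The sample size section allows for "an estimated dropout ratio of 10.0" per cent.

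**The concern.** A worst-case rule is meant to guarantee that missing data cannot help the treatment. This one gives no such guarantee.

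For time to first analgesic, a missing esmolol value is scored as the best result seen while the plan calls it the worst. A missing control value is scored as best too. The bias therefore follows whichever arm loses more values, and the label hides this.

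For mean blood pressure and heart rate the maximum is simply not a defined worst case.

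For the primary endpoint the value is unfavourable to the individual patient, but the trial tests a difference between arms. Imputing the maximum in the control arm favours esmolol. Even one imputed value moves the estimate, because it sits at the extreme of the distribution. A reader told that the analysis was worst case would draw the wrong conclusion.

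The direction is right where higher is worse: pain scores, PACU opioid consumption, time in hypotension and PACU stay.

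**Working it through.** **Inputs.** From Sample Size Determination and Power: means 7.98 (control) and 5.59 (esmolol), SD 3.24, two-sided 5%, power 80%, 10% dropout, 32 per arm. From Primary Outcome: Wilcoxon-Mann-Whitney test. The number and split of missing values are not in the protocol and are assumed; splits are written control/esmolol. The maximum is taken over all patients.

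**The plan's own figure.** Difference = 7.98 − 5.59 = 2.39. Per arm, n = 2 × (1.960 + 0.842)² × (3.24/2.39)² ≈ 28.8, so 29. Then 29 × 1.10 = 31.9, so 32. The stated size reproduces.

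**Primary endpoint.** There were 20,000 simulated trials per scenario, with values missing completely at random within arm and a tie-corrected test. Normal, gamma and lognormal data were matched to the stated means and SD. The skewed models matter because the protocol itself doubts normality, and the normal model puts 4.2% of esmolol patients below zero.

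| Missing | Data | Difference with the rule | Power with the rule |
|---|---|---|---|
| 0/0 | normal | 2.39 | 80% |
| 0/1 | normal | 2.10 | 72% |
| 1/0 | normal | 2.61 | 85% |
| 0/0 | lognormal | 2.39 | 93% |
| 0/1 | lognormal | 2.00 | 88% |
| 1/0 | lognormal | 2.71 | 95% |

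Check by hand for normal data: one imputed value M moves its arm mean by (M − arm mean)/32. For esmolol, M = 5.59 + 32 × 0.29 = 14.9. For control, M = 7.98 + 32 × 0.22 = 15.0. Both imply an average maximum near 15.

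With six missing and normal data, 2/4 gives 1.66 and 4/2 gives 2.66. Available-data analysis stays near 2.39 in every split.

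| Equal loss | Data | Power, available data | Power with the rule | Loss (points) |
|---|---|---|---|---|
| 1/1 | normal | 79.3% | 76.6% | 2.7 |
| 1/1 | gamma | 86.7% | 84.5% | 2.2 |
| 1/1 | lognormal | 91.8% | 90.4% | 1.4 |
| 3/3 | normal | 76.1% | 65.5% | 10.6 |
| 3/3 | gamma | 83.7% | 74.9% | 8.8 |
| 3/3 | lognormal | 90.6% | 84.0% | 6.6 |

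Three per arm corresponds to the full 10% dropout and is an upper end.

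**Type I error, two-sided, with the rule.** By split, counting either arm as the one losing more: 1/1 4.1%, 0/2 6.0%, 3/3 2.3%, 2/4 3.9%, 1/5 9.7%, 0/6 20.8%. Weighting by the chance of each split when loss is unrelated to arm:

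- Two missing: 0.508 × 4.1 + 0.492 × 6.0 = 5.0%.
- Six missing: 0.328 × 2.3 + 0.476 × 3.9 + 0.172 × 9.7 + 0.024 × 20.8 = 4.8%.

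So the average error holds; only an imbalance between arms breaks it.

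**Time to first analgesic.** With no true effect, take P(esmolol longer) + ½ P(tie), imputed values being tied at the maximum. This uses ranks only.

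- 0/1: the imputed value beats or ties a control value with score 1 − 0.5/63 = 0.9921. Result: (31 × 0.5 + 0.9921)/32 = 0.515.
- 0/2: (30 × 0.5 + 2 × (1 − 0.5/62))/32 = 0.531.
- Equal loss: 0.500.

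**The case against.** The strongest reply has four parts.

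**Few primary values will be missing.** The Monitoring section has all intraoperative data recorded, and the withdrawal section places withdrawal of consent before anaesthesia or in PACU. The breach-of-protocol section says stopping events will be collected and analysed, and does not say that remifentanil recording ends. This stands. It limits the size of the effect, not its direction.

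**The three-per-arm case assumes that dropouts are imputed.** The exclusion criteria remove withdrawn and converted patients, and no data are stored after withdrawal, so dropouts may leave the analysis altogether. This also stands in part: the figure is an upper end and depends on a reading that the intention-to-treat statement contradicts.

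**The likelier imbalance works against esmolol.** The one arm-related cause of loss that the protocol names is instability attributable to study drug. With excess loss under esmolol, false positives in its favour are about 1.5% (0/1), 0.5% (0/2) and 0.4% (2/4), against a nominal 2.5%. That is conservative for superiority. But withdrawal, conversion and loss of the NOL signal can fall either way. Excess loss in control gives 5.2% (2/0), 3.9% (4/2) and 9.9% (5/1). A rule whose protection depends on which arm loses data is not reliably conservative, and when it does err against esmolol it costs power and biases the estimate.

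**The certain error is secondary and small, and the blood pressure and heart rate point is minor.** The shift to 0.515 or 0.531 is indeed small. Blood pressure and heart rate are captured electronically, so a wholly missing mean is unlikely, and hypotension and bradycardia have their own endpoint. The stated rule still covers these endpoints and is still wrong or undefined for them. It is a fixed rule, not detail left to a statistical analysis plan.

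**Conclusion.** The concern holds, and the rule should be corrected before analysis.

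- **Time to first analgesic:** the worst-case label is wrong. This follows from the protocol's own hypothesis and needs no assumption. The numerical effect is small and vanishes with equal loss.
- **Mean blood pressure and heart rate:** the rule defines no worst case.
- **Primary endpoint:** the rule is not reliably conservative. One missing value shifts the estimated difference by about 0.2 to 0.4 mcg/kg/h, in a direction set by the arm it falls in. Equal loss costs 1 to 3 points of power with one missing per arm and about 7 to 11 with three. Type I error averages about 5% if loss is unrelated to arm.

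Confidence is high for the direction error. The size for the primary endpoint rests on an assumed number missing, on loss unrelated to outcome within arm, and on reading the maximum as the overall one.

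**What to change.** Withdraw maximum-value imputation as the main analysis and state instead:

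1. **Primary endpoint:** analyse the recorded remifentanil of all randomised patients, using available data, or multiple imputation where a value is truly missing.
2. **Time to first analgesic:** analyse as time to event, censored at PACU discharge. A patient who needs no analgesic in PACU is censored, not missing; the present text does not separate the two.
3. **Sensitivity analysis only:** extreme-value imputation, with the unfavourable direction written down for each endpoint. For a comparison, a strict worst case gives unfavourable values to esmolol and favourable values to control.
4. **Whose values count as missing:** reconcile the post-recruitment exclusions in the Exclusion criteria, the withdrawal section and the statement that no data are stored after withdrawal with the intention-to-treat commitment.

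The cost is a few lines of statistical text and a little more analysis work. No extra patients are needed.

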### *Secondary Outcome*

Intraoperative and postoperative data collected in the groups will be compared using parametric (Student t-test) or nonparametric tests (Mann-Withney U test) depending on the type of variables and their distribution, and a chi-square test will be used for proportion. Data collected over time on categorical variables or on those which are not normally distributed will be analyzed with non-parametric tests.

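### The only significance level, 0.05, is not confined to the primary endpoint, so each secondary outcome, including the predicted PACU benefits, can be declared significant without adjustment

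*Protocol*

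**What the plan says.** The protocol names one primary endpoint, intraoperative remifentanil per kilogram and hour (section D, Primary endpoint). The sample size rests on that endpoint alone: "With an alpha risk of 5%, a power of 80.0%, a two-tailed test, and an estimated dropout ratio of 10.0" (the last figure is a percentage; section E, Sample Size Determination and Power).

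Section E, Statistical Methods, covers the whole analysis. It promises that "Risk differences or mean differences with 95% confidence intervals will be reported for all outcomes", and the next sentence is "The alpha value will be set at 0.05 to establish statistical significance". Only after this do the Primary Outcome and Secondary Outcome subsections begin. The latter states: "Intraoperative and postoperative data collected in the groups will be compared using parametric (Student t-test) or nonparametric tests", with a chi-square test for proportions. It sets no other significance level, no testing order and no exploratory status.

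Section D, Secondary endpoints, has 11 bullets. Many are compound, for example "Total time and time weighted average with NOL value above > 25". Section B, Hypotheses, predicts a direction for several of the recovery-room outcomes. The prediction reads "we expect a longer time to first opioid, a lower pain score on arrival, a lower opioid consumption, a reduced incidence of PONV". Section B predicts a shorter stay as well.

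**The concern.** A level that establishes significance, stated once for the whole analysis and followed by tests of all secondary data, lets any secondary result with p below 0.05 be reported as established. The more comparisons there are, the likelier it is that at least one crosses the line by chance.

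The PACU outcomes are the most exposed. They are the clinically attractive claims, they carry directional predictions, and the sample size was not set for any of them. The same rule covers the haemodynamic outcomes, for which section B predicts no impact, so a chance signal of harm could also be called significant.

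**Working it through.** **The plan's own figure.** The inputs are the means ("we assumed a mean intraoperative remifentanil consumption of 5.59 mcg.kg-1.h-1 and 7.98"), a difference of 7.98 − 5.59 = 2.39, and an SD of 3.24 ("with a combined standard deviation of" ±3.24). With two-sided 5% and 80% power:

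n = 2 × (3.24 / 2.39)² × (1.960 + 0.842)² = 28.8, rounded up to 29 per group.

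Inflating by 10% gives 29 × 1.1 = 31.9, so 32, as stated. The whole 5% is thus spent on one endpoint with one test. The protocol states no error rate for the secondary outcomes.

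**Number of secondary comparisons (section D).** One test per bullet gives 11. Splitting every component gives:

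| Group of endpoints | Count |
|---|---|
| NOL response: 2 stimuli × (maximum, area under the curve) | 4 |
| Mean BP, mean HR | 2 |
| Four vasoactive drugs × (dose, time-weighted average) | 8 |
| NOL above 25: total time, time-weighted average | 2 |
| Hypotension and two bradycardia thresholds × 2 metrics | 6 |
| PACU: first analgesic 1, opioid use 1, pain at rest and under stress 2, SIA score 1, PONV and antiemetics 2, length of stay 1 | 8 |
| **Total** | **30** |

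Section B predicts five PACU benefits: later first opioid, lower pain on arrival, lower opioid use, less PONV and a shorter stay.

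**Chance of at least one false positive, all null hypotheses true.** For k independent tests it is 1 − 0.95^k:

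- k = 5: 1 − 0.95⁵ = 22.6%
- k = 11: 1 − 0.95¹¹ = 43.1%
- k = 30: 1 − 0.95³⁰ = 78.5%, with 30 × 0.05 = 1.5 false positives expected

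For correlated tests the calculation takes equicorrelated normal test statistics, each two-sided at 1.96. The protocol gives no correlations, so these are assumptions:

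| Common correlation | 5 tests | 11 tests | 30 tests |
|---|---|---|---|
| 0 | 23% | 43% | 79% |
| 0.3 | 21% | 37% | 66% |
| 0.5 | 18% | 30% | 51% |
| 0.6 | 17% | 26% | 42% |

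A single common correlation is crude, because two metrics of one quantity are closer to each other than to other endpoints. With correlation 0.5 to 0.9 within an endpoint family and 0 to 0.3 between families, 30 tests give 57% to 76%.

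**If some effects are real.** A false positive can then arise only among the remaining nulls.

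- Suppose the 16 haemodynamic and vasoactive-drug comparisons (2 + 8 + 6) reflect true effects. That leaves 30 − 16 = 14 nulls: 1 − 0.95¹⁴ = 51% if independent and 35% at common correlation 0.5.
- Suppose section B is right, so that NOL and PACU effects are real and haemodynamics are unaffected. The 16 are then the nulls: 56% if independent and about 38% to 53% with the family-structured correlations above.

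**The case against.** **This is an omission that belongs in the SAP.** A level of 0.05 is conventional and agrees with the sample-size section. An unseen SAP may add a multiplicity rule or an exploratory label, and the absence of one from a protocol would not by itself be a finding. What remains is that this protocol fixes a rule: 0.05 establishes significance, in text that governs both outcome subsections, and the secondary data are then tested. The point concerns that sentence.

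**The scope is inferred.** This is correct. The significance sentence does not mention every outcome; the neighbouring sentence on intervals does. The wider scope follows from placement and from the lack of any other level. It is the ordinary reading, but a reading.

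**A hierarchy already exists.** There is one primary objective, endpoint and test, and the PACU benefits are worded as expectations. This fully protects the primary result. It does not say what a secondary p-value below 0.05 may be called.

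**The probability can be overstated.** A reader might infer that at least one false significant secondary result is more likely than not. The protocol does not support that without conditions. It needs most components split into separate tests, nearly all nulls true and correlation no more than moderate. The chance is 43% or less at one test per bullet and 42% for 30 tests at correlation 0.6. Many of the 30 are near-duplicates, such as total time and time-weighted average of one state, or the two nested heart-rate thresholds. Nor is it plausible that all nulls are true: the Background says esmolol can lower BP and HR, and section F lists hypotension and bradycardia as adverse reactions. If those effects are real, the chance among the rest is about half or less.

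**Conclusion.** The point holds in a limited form. Read in the ordinary way, the protocol allows each secondary outcome to be declared significant at an unadjusted 0.05, and nothing in it marks those results as exploratory.

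The size depends on how the endpoints are counted and on assumed correlations. If every secondary null is true, the chance of at least one false positive is about 30% to 43% for 11 tests (correlation 0.5 to 0), 42% to 79% for 30 tests (0.6 to 0) and 17% to 23% for the five PACU predictions (0.6 to 0). Even the lowest figure, 17%, is more than three times the nominal 5%.

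The primary endpoint's 5% error rate and the sample size are not affected. The point bears only on how secondary results may be claimed.

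**What to change.** In section E, Statistical Methods, confine the 0.05 significance statement to the primary endpoint. Add that secondary outcomes will be reported as estimates with the 95% confidence intervals already promised, unadjusted for multiplicity, labelled exploratory and without claims of significance. Amend the Secondary Outcome subsection to match, and do so before unblinding.

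The cost is one or two sentences. No endpoint is dropped, haemodynamic results are still reported in full and the sample size does not change. The downside is that no secondary result can be called statistically significant.

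If confirmatory secondary claims are wanted, a few PACU endpoints could be named and tested under a multiplicity procedure, for instance Holm after a significant primary result. That is optional and one choice among several.
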